5.2 Rule of exclusion criteria of analysis sets

The protocol deviations defined for this study are the followings:

Table 1 Protocol deviations that cause patients to be excluded

Deviation Code	Text Description	Severity/ Analysis Classify action Code
E01	Any medical or neurological condition other than AD that could explain the patient's dementia at baseline.	1
E02	Current diagnosis of probable vascular dementia according to National Institute of Neurological Disorders & Stroke and AIREN criteria at baseline.	1
E03	A current DSM-IV diagnosis of major depression, unless successfully treated with a stable dose of an antidepressant without anticholinergic properties for at least 4 weeks at baseline	49
E04	Any other DSM-IV Axis1 diagnosis interfering with evaluation of patient's response to study medication including other primary neurodegenerative dementia, schizophrenia or bipolar disorder at baseline.	49
E05	A current diagnosis of active, seizure disorder at baseline	49
E06	A history or current diagnosis of severe cerebrovascular disease at baseline	49
E07	A current diagnosis of severe or unstable cardiovascular disease, hypertension, diabetes at baseline	49
E08	A current diagnosis of bradycardia (< 50 bpm), sick-sinus syndrome, or conduction defects (sino-atrial block, second or third degree atrio-ventricular block) at baseline	49
E09	A current diagnosis of acute, severe, or unstable asthmatoïd conditions at baseline	49
E10	A current diagnosis of active, uncontrolled peptic ulceration or gastro-intestinal bleeding within the last 3 months from baseline	49
E11	Clinically significant urinary obstruction at baseline	49
E12	Patients with extrapyramidal disorders	49
E13	Patient with complication of gastrointestinal (GI) adverse events during oral ChE inhibitors treatment except for GI adverse events caused by drugs other than oral ChE inhibitors	49
E14	Patients with low body weight as judged by the investigators at Visit 1 and/or 2 date	49
E15	Current diagnosis of an active skin lesion/disorder that would influence to the adhesion and potential skin irritation of the patch at baseline	49
E16	A disability that may prevent the patient from completing all study requirements at baseline	49
E17	Patients with a history of hypersensitivity to any ingredients of rivastigmine or carbamate derivatives	49

E18	Patients who have taken rivastigmine anytime in the past (Please consider partial dates)	49
E19	Any rehabilitation day care and day service during 4 weeks or more prior to efficacy assessment at baseline must not be changed significantly with content and frequency (new start/discontinuation)	49
E20	Taken any investigational drug (including investigational biologics) in the 90 days prior to baseline or within 5 half-lives of the compound, whichever is longer;	49
E21A	Use of donepezil > 5 mg/day 4 weeks prior to baseline (Visit 2)	1
E21B	Any ChEIs(except donepezil,galantamine),selegiline,centrally acting anticholinergic drug,olanzapine or tricyclic & tetracyclic antidepressants,lithium during 4 weeks prior to efficacy assessment at V2	1
E21C	Change of dosage, frequency of donepezil, galantamine, memantine during the 4 weeks prior to efficacy assessment at baseline (V2)	1
E21D	Succinylcholine-type muscle relaxants, lithium during the 2 weeks prior to efficacy assessment at Visit 2	49
E21E	Newly used benzodiazepine-type hypnotics of short duration, newly used or irregularly used zolpidem tartrate and zopiclone within 24 hours prior to efficacy assessment at Visit 2	49
E21F	Change of dosage and frequency of other specified drugs during the 4 weeks prior to efficacy assessment at baseline (V2)	49
E22A	Total bilirubin 3.0 mg/dL or above at Visit1	49
E22B	AST (SGOT) and/or ALT (SGPT) 3 x ULN or above at Visit 1	49
E22C	Plasma creatinine 2.0 mg/dL or above at Visit1	49
E23	History of malignancy treated or untreated within past 5 years with exception of localized basal cell carcinoma of skin.	49
E24	Patients diagnosed by investigator as unsuitable for inclusion in this clinical study	49

I01	No written informed consent from patient and/or his/her Caregiver at V1	8
I02	Aged ≤49 or ≥86	49
I03	Out patient status at baseline	49
I04	Female with child- bearing potential	49
I05	No diagnosis of mild to moderate AD (dementia of the Alzheimer's type) according to DSM-IV criteria	1
I06	No clinical diagnosis of probable mild to moderate AD as per NINCDS-ADRDA criteria	1
I07	A MMSE score of < 10 or > 23 at Visit1 & V2	1
I08A	Patients are not currently on the oral monotherapy (donepezil, 5 mg), within 4 weeks prior to baseline visit.	49
I08B	Patients are not currently on the galantamine (16-24 mg) within 4 weeks prior to baseline visit.	49
I09	"Date of MMSE examination " provided must be within six months and 14 days prior to screening visit date.	49

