#### **4.1 Inclusion criteria**

Patients/subjects eligible for inclusion in this study must fulfill all of the following criteria:

1. Written informed consent of the patient and legal representative will be obtained before any assessment is performed (MUST be signed by the legal representative if a signed informed consent from patients is difficult, consent can only be obtained from the patients orally) at Screening.
2. Patients within the age of 50-85 years at Baseline.
3. Outpatient status at Baseline.
4. Males and females not of child-bearing potential.
  - Women are considered post-menopausal and not of child bearing potential if they have had 12 months of natural (spontaneous) amenorrhea with an appropriate clinical profile (e.g. age appropriate, history of vasomotor symptoms) or have had surgical bilateral oophorectomy (with/without hysterectomy) or tubal ligation at least six weeks previously.
5. A diagnosis of dementia of the Alzheimer's type according to the DSM-IV criteria.
6. A clinical diagnosis of probable AD according to National Institute of Neurological and Communicative Disorders and Stroke - Alzheimer's Disease and Related Disorders Association (NINCDS-ADRDA) criteria and meeting any of following criteria.
  - Brain scan (magnetic resonance imaging [MRI], or computed tomography [CT]) were met diagnosis criteria conducted within 3 years prior to baseline (Imaging within 1 year prior to baseline is preferable).
  - Positron emission tomography (PET) or single photon emission computed tomography (SPECT) was met diagnosis criteria conducted within 3 years prior to baseline visit; as long as in the past a brain scan (MRI or CT) was also met (Imaging within 1 year prior to baseline is preferable).
7. An MMSE score of  $\geq 10$  and  $\leq 23$  at screening and baseline.
8. Patients are currently on the oral monotherapy (donepezil, 5 mg), or galantamine (16-24 mg) for 4 weeks prior to baseline visit.
9. Patients who could not receive treatment benefits of previous oral ChEIs can be defined by meeting the following criteria, either 9-1, 9-2, or both.
  - 9-1. Patients who are not responding to the previous treatment can be defined if the patients meet at least one of these conditions at screening and baseline
    - Patients who declined  $\geq 2$  points of MMSE despite of treatment of other oral ChE inhibitors within initial 3-month and continued to show insufficient treatment effect until at baseline.

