## 4.2 Exclusion criteria

Patients fulfilling any of the following criteria are not eligible for inclusion in this study. No additional exclusions may be applied by the investigator, in order to ensure that the study population will be representative of all eligible patients.

1. Any medical or neurological condition other than AD that could explain the patient's dementia (e.g., abnormal thyroid function tests, vitamin B12 or folate deficiency, posttraumatic conditions, syphilis, head injury, Huntington's disease, Parkinson's disease, subdural hematoma, normal pressure hydrocephalus, brain tumor) at baseline;
2. A current diagnosis of probable or possible vascular dementia according to the National Institute of Neurological Disorders and Stroke and the Association Internationale pour la Recherche et l'Enseignement en Neurosciences criteria (NINDS-AIREN) at baseline;
3. A current DSM-IV diagnosis of major depression, unless successfully treated with a stable dose of an antidepressant without anticholinergic properties for at least 4 weeks at baseline;
4. Any other DSM-IV Axis 1 diagnosis that may interfere with the evaluation of the patient's response to study medication, including other primary neurodegenerative dementia, schizophrenia, or bipolar disorder at baseline;
5. A current diagnosis of active, seizure disorder at baseline;

6. A history or current diagnosis of severe cerebrovascular disease (e.g., stroke, transient ischemic attacks, aneurysms) at baseline;
7. A current diagnosis of severe or unstable cardiovascular disease (e.g., cardiac failure congestive, angina unstable), hypertension, diabetes at baseline;
8. A current diagnosis of bradycardia (< 50 bpm), sick-sinus syndrome, or conduction defects (sino-atrial block, second or third degree atrio-ventricular block) at baseline;
9. A current diagnosis of acute, severe, or unstable asthmatoïd conditions (e.g., severe chronic obstructive pulmonary disease (COPD) at baseline;
10. A current diagnosis of active, uncontrolled peptic ulceration or gastro-intestinal bleeding within the last 3 months from baseline;
11. Clinically significant urinary obstruction at baseline;
12. Patients with extrapyramidal disorders (e.g., Parkinson's disease, Parkinson's syndrome).

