hydrochloride and propiverine hydrochloride, tolterodine tartrate, solifenacin and imidafenacin etc), Yokukan-san, Yokukansankachimpahange during the 4 weeks prior to efficacy assessment at baseline;

- Succinylcholine-type muscle relaxants, lithium during the 2 weeks prior to efficacy assessment at baseline;
- Newly used benzodiazepine-type hypnotics of short duration, newly used or irregularly used zolpidem tartrate and zopiclone within 24 hours prior to efficacy assessment at baseline;

22. Result(s) of laboratory tests at the screening visit:

- total bilirubin 3.0 mg/dL or above;
- AST (GOT) and/or ALT (GPT) 3  $\times$ ULN or above;
- serum creatinine 2.0 mg/dL or above;

23. History of malignancy of any organ system, treated or untreated, within the past 5 years whether or not there is evidence of local recurrence or metastases, with the exception of localized basal cell carcinoma of the skin;

24. Patients who, in the opinion of the investigator, will be otherwise unsuitable for inclusion in this clinical study (e.g., an advanced, severe, progressive, or unstable disease of any type that may interfere with efficacy and safety assessments or put the patient at special risk);

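### Three code 1 rows in SAP Table 1 (E02, I07, E21B) do not match the protocol criteria they implement, so per-protocol membership can be wrong

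*SAP*

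**What the plan says.** SAP Section 5.2 gives each deviation a severity code in Table 1. Tables 2 and 3 then say what the code does. Codes 0, 1, 6 and 8 remove a patient from the PP set. Code 49 means that the deviation is reported and the patient stays in every analysis.

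- **MMSE range.** Protocol Section 4.1, criterion 7, requires a score of 10 to 23 "at screening and baseline". SAP row I07 (code 1) reads "A MMSE score of < 10 or > 23 at Visit1 & V2".
- **Vascular dementia.** Protocol Section 4.2, criterion 2, excludes "A current diagnosis of probable or possible vascular dementia". SAP row E02 (code 1) reads "Current diagnosis of probable vascular dementia according to National Institute" and continues with the name of the criteria; possible does not appear.
- **Lithium.** In Protocol Section 4.2, criterion 21, the 4-week list does not contain lithium. Lithium has its own line: "Succinylcholine-type muscle relaxants, lithium during the 2 weeks prior to efficacy assessment at baseline". SAP row E21B (code 1) adds it to the 4-week list: "tricyclic & tetracyclic antidepressants,lithium during 4 weeks prior to efficacy assessment at V2". SAP row E21D (code 49) repeats it with the 2-week window.

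SAP Section 4, which lists changes from the protocol analyses, declares none of these differences. Protocol Amendment 1 does not touch these three criteria.

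**The concern.** A deviation table should be the logical negation of the eligibility criteria, or should say where it departs from them. These three rows do neither. As worded, E02 and I07 can leave protocol-ineligible patients in the PP set, and E21B can take a patient out who broke no protocol rule.

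The PP set carries the first supportive MMRM analysis of the primary endpoint (SAP Section 2.5.4), an additional analysis of the secondary efficacy variables (SAP Section 2.6.1) and the added responder rate (SAP Section 4, item 1). There is also a reporting side: a patient who breaches criterion 7 at one visit only, or who has possible vascular dementia, matches neither I07 nor E02 as written and may not be listed as a deviation at all.

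**Working it through.** The plan states no figure to reproduce, so the check compares each rule with its counterpart.

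**I07.** Write A for out of range at Visit 1 (screening) and B for out of range at Visit 2 (baseline).

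- Protocol: eligible means not A and not B. Ineligible is therefore A or B.
- I07 read literally: A and B.

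Take the boundary scores 9, 10, 23 and 24 at each visit, giving 4 × 4 = 16 combinations. Scores 9 and 24 are out of range; 10 and 23 are in range.

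- In range at both visits: 2 × 2 = 4, eligible.
- Out of range at both visits: 2 × 2 = 4, ineligible and flagged.
- Out of range at exactly one visit: 2 × (2 × 2) = 8, ineligible and not flagged.

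So 4 + 8 = 12 combinations are ineligible, and literal I07 catches 4. These are counts of score combinations, not proportions of patients.

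**E02.** The protocol set is probable plus possible. The SAP set is probable. The difference is the patient with possible but not probable vascular dementia, whom E02 does not flag. Two other code 1 rows might: E01 (another condition that could explain the dementia) and I06 (no clinical diagnosis of probable AD). Neither names possible vascular dementia, and the protocol keeps it as a separate criterion, so capture is not assured.

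**Lithium.** Take 2 weeks as 14 days and 4 weeks as 28 days, counted back from the baseline efficacy assessment.

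| Last lithium use before baseline | Protocol criterion 21 | E21B (code 1) | E21D (code 49) | PP set under these two rows |
|---|---|---|---|---|
| 1 to 14 days | ineligible | yes | yes | removed by code 1, although code 49 says keep |
| 15 to 28 days | no deviation | yes | no | removed |
| 29 days or more | no deviation | no | no | kept |

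The middle row is the mismatch with the protocol. The first row is a conflict within the SAP. Table 2 excludes on any code 1, so the code 49 that E21D gives to lithium can never take effect.

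Now delete lithium from E21B and change nothing else. The 15 to 28 day case is then kept, in line with the protocol. The 1 to 14 day case carries only code 49 and is also kept, although the protocol excludes it, unless some other code applies.

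**The case against.** **I07 may only be shorthand.** Its ampersand may simply compress the protocol's own phrase, meaning that the score is checked at both visits. Table 1 is loosely drafted elsewhere: I03 names outpatient status, which is the requirement and not the breach; S02 describes the correct 1-step regimen and still carries code 1; E19 states the rule. This stands in part, and nobody can say that the literal reading will be programmed. On the other side, E14 in the same table uses *and/or* for the two visits, so the authors had a form of words for either visit. An ambiguous row that decides analysis-set membership should be cleared up whichever reading was meant.

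**A patient must first be enrolled in error.** A reader might infer that ordinary retest variation around an MMSE of 23 will put ineligible patients into the PP set. The documents do not support that. Protocol Table 6-1 has eligibility checked at both visits, so a patient who drifts out of range at Visit 2 should be a screening failure. Protocol Section 8.1 requires full verification of adherence to the eligibility criteria. Contamination needs an enrolment mistake, for which the documents give no rate.

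**Keeping some ineligible patients is by design.** Most eligibility breaches carry code 49 and stay in the PP set. That is true, but it does not explain these rows: the SAP gave MMSE range and vascular dementia code 1, so it meant to remove such patients.

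**The consequence is small.** The PP analyses are supportive or additional, and the p-values for the primary endpoint and its supportive analyses are descriptive. This stands.

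**Conclusion.** The three mismatches are in the current text and can be checked word against word. E02 and the lithium rows need no interpretation. I07 is wrong if read literally and ambiguous otherwise.

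The effect is confined to PP membership and to the deviation listing. The full analysis set drops only codes 0, 6 and 8 (SAP Table 2), so the primary analysis does not move. The number of patients affected is likely small and cannot be derived from the documents.

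A reader might go further and conclude that the PP set does contain ineligible patients, or that the PP estimate is biased. The documents show only that the rules permit misclassification, in either direction. They do not show that it occurred. This is a minor consistency point, worth correcting because the correction costs almost nothing.

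**What to change.** In SAP Table 1:

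1. **I07:** out of range at Visit 1 *or* Visit 2.
2. **E02:** add *or possible* after probable.
3. **Lithium:** reconcile the window and the severity code across E21B, E21D and protocol exclusion criterion 21, and list lithium in one row only. The documents do not settle which code was intended, so the sponsor has to decide. Removing lithium from E21B without revisiting the code in E21D would leave protocol-ineligible use within 2 weeks in the PP set.

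If any departure from the protocol is deliberate, declare it in SAP Section 4. The cost is a few wording edits and a matching check of the deviation programming. Both documents already require major deviations to be specified before database lock, so the edits belong there. No new data are needed.

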Analysis Set	PD severity codes that cause a subject to be excluded	Criteria that cause a subject to be excluded
FAS	0, 6, 8	Enrolled but no study drug received
PPS	0, 1, 6, 8	NA
SAF	8	

Table 3 Severity codes with action taken

Code	Action
0	Exclude from all efficacy analysis
1	Exclude from per protocol analysis
6	Exclude from Main Analysis Set

8	Exclude from all analysis
49	Report relevant protocol deviation – include in all analyses

5.3 SAS codes for statistical analyses.

5.3.1 Mixed Model Repeated Measures (MMRM) analysis

The change from baseline in MMSE total score will be analyzed using a mixed model repeated measures (MMRM) model. The model will contain visit as a fixed effect, baseline MMSE score as a covariate and subject as a random effect. An unstructured covariance matrix should be used.

```
proc mixed data = xxx ;
  class visit subjid;
  model chg = visit base /noint ddfm = KR alpha = 0.05;
  repeated visit /type = UN subject = subjid ;
  lsmeans visit /cl;
run;
```

where,

chg: change from baseline in MMSE total score

visit: study visits as per protocol assessment schedule,

base: baseline MMSE score

subjid: subject identifier.

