### **6.4.1 Mini-Mental state examination (MMSE)**

MMSE will be conducted at Visit 1, 2, 4 and 8 (refer [Table 6-1](#)). MMSE at premature discontinuation will not be conducted if patient discontinues because of adverse event.

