##### **9.4.2 Statistical model, hypothesis, and method of analysis**

The change from baseline in MMSE total score will be analyzed using a mixed model repeated measures (MMRM) model. The model will contain visit as a fixed effect, baseline MMSE score as a covariate and subject as a random effect. An unstructured covariance matrix will be used to model the within-subject error. The estimated mean change at Week 24 along with a two-sided 95% confidence interval and p-value will be presented. P-values will be used in descriptive manner.

Further, the MMSE total score and change from baseline will be summarized using standard descriptive statistics by visits.

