2.5.1 Primary endpoint

The primary variable is change from baseline at Week 24 in the total score of 11 items included in the Mini-Mental State Examination (MMSE) for the FAS. Of note, the primary analysis will include all patients in the FAS population irrespective of the treatment regimen.

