2.5.2 Statistical hypothesis, model, and method of analysis

The change from baseline in MMSE total score will be analyzed using a mixed model repeated measures (MMRM) model. The model will contain visit as a fixed effect, baseline MMSE score as a covariate and subject as a random effect. An unstructured covariance matrix should be used. The estimated mean change at Week 24 along with a two-sided 95% confidence interval and p-value will be tabulated and presented graphically. P-values will be used in descriptive manner.

Further, the MMSE total score and change from baseline will be summarized using standard descriptive statistics by visits.

In addition, the primary endpoint will be summarized and analyzed by subgroups specified in [Section 2.2.1.1](#).

The MMRM model of subgroup analysis will contain visit, subgroup (categories) and visit*subgroup as fixed effects, baseline MMSE score as a covariate and subject as a random effect. An unstructured covariance matrix should be used. The estimated mean change at Week 24 along with a two-sided 95% confidence interval and p-value will be presented. P-values will be used in descriptive manner. Figures will only be provided for selected subgroup analysis as specified in [Section 2.2.1.1](#).

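### The primary MMRM shares one baseline slope across Week 8 and Week 24 and fixes no reporting baseline, so the Week 24 mean can keep most of any drop-out bias that runs through baseline MMSE

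*SAP*

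**What the plan says.** SAP 2.5.2 states: "The model will contain visit as a fixed effect, baseline MMSE score as a covariate and subject as a random effect". Protocol 9.4.2 gives the same model and adds: "An unstructured covariance matrix will be used to model the within-subject error". The code in SAP 5.3.1 agrees with both texts: "model chg = visit base /noint ddfm = KR alpha = 0.05", then "lsmeans visit /cl". There is no visit-by-baseline term and no option that sets the baseline at which the visit means are evaluated. The subgroup code in SAP 5.3.2 has the same two features.

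On timing, Protocol 6.4.1 says: "MMSE will be conducted at Visit 1, 2, 4 and 8". The scheduled post-baseline values are therefore Week 8 and Week 24 only. The same section says MMSE is not done when a patient stops because of an adverse event. FAS membership (SAP 2.2) needs a baseline and some post-baseline assessment of any kind, not an MMSE. SAP 2.5.3 relies on missing-at-random and allows no other imputation for the primary analysis. SAP section 4, point 3, re-maps the last records of discontinued patients to the nearest planned visit.

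**The concern.** In a randomised comparison the reference baseline cancels when arms are subtracted. Here there is one arm and the Week 24 least-squares mean is the primary result, so any shift in the reference baseline, multiplied by the fitted slope, passes straight into it.

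Two features could let drop-out in.

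- **Reporting baseline.** If the software averages baseline over analysed records, a patient with both MMSE visits counts twice, a patient with Week 8 only counts once, and an FAS patient with no post-baseline MMSE does not count. The reference then drifts from the FAS mean towards the completers.
- **Common slope.** Week 8 falls four weeks after the planned step to 18 mg/day and Week 24 falls twenty weeks after it. If change relates differently to baseline at the two visits, a shared slope is wrong at both and the Week 24 adjustment is wrong with it.

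The MMRM is the analysis meant to deal with drop-out under missing-at-random. At stake is how much of the baseline-related part it removes.

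**Working it through.** **1. The plan's own figure.** n = (1.96 × SD / half-width)² = (1.96 × 3.0 / 0.6)² = 96.04, rounded up to 97, as in Protocol 9.8. The implied loss is 1 − 97/120 = 19.2%.

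**2. Inputs.** From the documents: SD of change 3.0, loss about 19%, baseline MMSE 10–23, half-width 0.6. Assumed, because the documents give none of them: baseline mean 16.8 and SD 3.3; SD of change 2.5 at Week 8; residual correlation 0.6; 8% missing at Week 8; slopes of change on baseline between −0.2 and +0.3; log odds of drop-out per 3.6 baseline points of 0, −0.5 (moderate) or −1.0 (strong). The record-mean default for the reporting baseline is also an assumption.

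**3. Equal slopes: hand calculation.** Only the reporting baseline matters:

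bias ≈ slope × (record mean − FAS mean).

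The record mean exceeds the FAS mean by 0.20 points (moderate) or 0.37 (strong). With slope −0.2 this gives −0.2 × 0.20 = −0.040 and −0.2 × 0.37 = −0.074. The completer mean under the strong link lies 17.37 − 16.84 = 0.53 above the FAS mean, giving −0.2 × 0.53 = −0.106. The share kept is about 0.37/0.53 = 70%.

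**4. Simulation.** Maximum-likelihood fits with unstructured covariance, 400,000 patients per scenario, 8% missing at Week 8 and 19% at Week 24. Entries are bias at Week 24 in MMSE points.

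| Drop-out link | Slopes (Wk 8, Wk 24) | Completer mean | SAP model | One slope, at FAS mean | Slope per visit, at FAS mean |
|---|---|---|---|---|---|
| moderate | −0.2, −0.2 | −0.056 | −0.038 | about 0.002 | within 0.007 |
| strong | −0.2, −0.2 | −0.104 | −0.071 | 0.001 | 0.001 |
| strong | −0.1, −0.2 | −0.106 | −0.091 | −0.045 | 0.001 |
| moderate | 0, 0.2 | 0.059 | 0.061 | 0.050 | within 0.007 |
| strong | 0, 0.2 | 0.108 | 0.109 | 0.090 | 0.000 |
| strong | −0.15, 0.15 | 0.078 | 0.107 | 0.137 | −0.003 |
| strong | 0, 0.3 | 0.163 | 0.166 | 0.134 | 0.004 |

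Share of completer bias kept: 0.071/0.104 = 68% with equal slopes, 0.091/0.106 = 86% with slopes −0.1 and −0.2, and essentially all with 0 and 0.2. A further simulation at the same missingness put the lower end at about 60%, with bias of about 0.03 to 0.14. Where the slopes have opposite signs, the planned model does worse than the completer mean.

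Both changes are needed. In the strong case with slopes 0 and 0.2, moving only the reporting baseline leaves 0.090. Adding only visit-specific slopes, still at the record mean, leaves 0.073.

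**5. How strong the links are.** Leavers start below completers by (completer mean − FAS mean)/0.19. Strong: 0.53/0.19 = 2.8 points. Moderate: the completer mean is 0.056/0.2 = 0.28 above the FAS mean, so 0.28/0.19 = 1.5 points.

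**6. Different assumptions.** With 20% missing (8% before Week 8), residual SD 2.8, correlation 0.5 and slopes differing by 0.2 to 0.5 between visits, the planned model's bias is 0.02–0.06 when leavers start 1.0 point lower and 0.04–0.14 when they start 2.3 points lower. The revised model stays within 0.003.

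**7. Against the half-width.** 0.038/0.6 = 6%; 0.061/0.6 = 10%; 0.109/0.6 = 18%; 0.166/0.6 = 28%. In trials of 120 patients, coverage of the planned 95% interval is about 93% under the strong link (0.932 and 0.937) and about 95% under the moderate one. The half-width is 0.57 with the revised model and 0.57–0.58 with the planned one.

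**8. When nothing happens.** If drop-out is unrelated to baseline, the planned model's bias is zero within simulation error (−0.004 to 0.003), even with slopes 0 and 0.2. It is also zero if change does not depend on baseline at either visit.

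**The case against.** The strongest reply is that this is a legitimate modelling choice. Protocol, SAP text and code agree, so there is no contradiction to repair. No success threshold is set, and SAP 2.5.2 says "P-values will be used in descriptive manner", so a shift of a tenth of a point decides nothing. The documents contain no slope on baseline and no link between baseline MMSE and leaving. The adverse events behind discontinuation that Protocol 1.1 describes are mainly skin reactions, which need not track MMSE. Patients who leave for other reasons are due the final-visit assessments (Protocol section 6), so many early leavers can supply an MMSE. SAP 2.2.1.1 also plans the MMRM by baseline MMSE category with a visit interaction, where unequal baseline effects would show.

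Most of this stands, and it limits the size and priority of the point. It does not remove it. The subgroup and completer analyses do not replace the primary estimate, and the completer t-test shares much of the same bias, so its agreement with the MMRM would not show robustness.

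Three stronger readings are tempting and unsupported.

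- A reader might infer that the Week 24 estimate is biased, or does not describe the FAS. That needs both links, and the documents establish neither.
- A reader might infer that the MMRM removes none of the baseline-related bias. With equal slopes it removed about a third.
- A reader might take SAP 2.5.1, "the primary analysis will include all patients in the FAS population irrespective of the treatment regimen", as a claim that every FAS patient supplies an MMSE. The sentence concerns titration: patients moved to the 3-step scheme stay in the primary analysis, whereas the per-protocol set excludes them. It says nothing about MMSE availability.

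**Conclusion.** The point holds as a conditional weakness and a free improvement. If drop-out and change both depend on baseline MMSE, and the software uses its usual record-mean default, the planned Week 24 estimate can keep roughly 60% to all of the baseline-related completer bias. Under the assumed slopes and links that is about 0.02 to 0.14 MMSE points, reaching about 0.17 at 19% missing with a strong link and slopes of 0 and 0.3. This is small to moderate beside the planned 0.6 half-width, with at most a slight loss of coverage. If either link is absent the bias is zero. The effect of the re-mapping in SAP section 4 on the record weights was not modelled.

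**What to change.** In SAP 2.5.2 and 5.3.1:

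- Define `cbase` as baseline MMSE minus the mean baseline of all FAS patients, one value per patient.
- Fit `model chg = visit visit*cbase / noint ddfm=KR` and request `lsmeans visit / cl at cbase=0`.
- Limit the visit factor to Week 8 and Week 24, the two post-baseline visits SAP 2.2.1.1 already names. Otherwise re-mapped discontinuation records could add sparse visit levels, each with its own slope. State what happens to MMSE records that re-map to any other visit.

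Use visit-specific baseline slopes in SAP 5.3.2 as well, and state the baseline at which those means are reported. Report how many FAS patients contribute a post-baseline MMSE. Since Protocol 9.4.2 has the common-slope model, list the change in SAP section 4.

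Cost: two lines of code, a few sentences and one extra parameter in the primary model. No new data are needed, and the simulated half-width does not widen.
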